### 10.1.2 Analysis of secondary endpoints

#### 10.1.2.1. Safety

Patients will be assessed for toxicities at each clinical evaluation. Toxicities will be graded according to CTCAE v5.0 standardized grading scales. The incidence of grade 3-5 toxicities will be reported. Patients will be assessed for toxicity as long as they are taking rucaparib, and patients will continue to be followed if rucaparib is discontinued for toxicity until the toxicities improve to grade 1 or resolve.

Toxicities will be reported as a tabulated table by type and grade.

#### 10.1.2.2. PSA progression-free survival (PFS)

A standard definition of PSA progression per PCWG3 will be used. PSA PFS will be defined as an increase in 25% over a nadir value, confirmed by a follow-up PSA at least 4 weeks apart. If patients are removed from study prior to PSA progression, then they will be censored at that time.

We will use the Kaplan-Meier method to estimate the median PSA PFS.

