**Study design**

The study is an open-label single arm Phase II trial. Eligible patients are those with metastatic hormone-sensitive prostate cancer (mHSPC) or high-risk biochemically recurrent prostate cancer (BCR). All patients must have a documented germline or somatic mutation in a homologous recombination DNA-repair gene (BRCA1, BRCA2, ATM, CHEK2, NBN, BRIP1, RAD50, RAD51C, RAD51D, PALB2, MRE11, FANCA, FANCB, FANCC, FANCD2, FANCE, FANCF, FANCG, FANCI, FANCL, FANCM). Germline genetic testing and molecular sequencing as a screening for eligibility will not be offered. A mandatory tumor biopsy will be performed prior to the start of therapy in all patients with metastatic disease (if tumor material is not successfully obtained at the time of biopsy, then archival material will be sought). A second, OPTIONAL tumor biopsy will take place after three months of therapy.

After enrollment, patients will be treated with rucaparib at the established dose of **600mg by mouth twice daily**. Patients will be followed monthly with clinic visits, safety labs (including CBC w/diff, Comp), PSA, and toxicity assessments. Treatment [with a minimum drug exposure of 12 weeks] will be continued until PSA progression (PCGW3 criteria) or clinical/radiographic progression (whichever comes first), or until unmanageable toxicity requiring drug cessation. Patients who remain on treatment

for >12 months can begin to have their clinic visits, safety labs (including CBC w/diff, Comp), PSA, and toxicity assessments every 3 months.

A trial schema for study treatment appears below:

Criteria for evaluation

Primary Endpoint

- PSA50 response rate, defined as a decline in PSA to  $\geq 50\%$  of baseline level, confirmed with a second measurement at least 4 weeks later (PCWG3).

Secondary Endpoints

- Safety/Tolerability, defined as incidence of CTCAE v5.0 grade  $\geq 3$  toxicities experienced by patients on the trial.
- PSA progression-free survival, defined as a time from initiation on rucaparib therapy until PSA increase of 25%, confirmed with another measurement at least 4 weeks later (PCWG3).
- Radiographic progression-free survival (PCWG3): time to radiographic or clinical progression or death, whichever comes first. Based on RECIST version

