Subjects will have circulating tumor DNA (ctDNA) examined by FoundationACT testing before starting treatment and at clinical progression while on rucaparib. We will report the incidence and describe the observed reversion mutation, a known mechanism of resistance to PARP inhibition.

Statistical  
method

Primary Analysis

The primary endpoint of this study is PSA50 response, defined as a decrease in the PSA to  $\geq 50\%$  less than the baseline PSA upon enrollment in the trial. The decrease must be confirmed by a second measurement at least 4 weeks apart. For purposes of meeting the primary endpoint, patients will be considered to have done so if they have a PSA50 response only while on therapy with rucaparib. PSA values will be measured monthly during the trial. All patients who take at least one dose of rucaparib will be considered evaluable for the primary endpoint. If patients do not have follow-up PSAs after initiation rucaparib therapy due to stopping therapy for toxicity or withdrawing consent, then they will be replaced.

Secondary Analysis

*Safety:*

Patients will be assessed for toxicities at each clinical evaluation. Toxicities will be graded according to CTCAE v5.0 standardized grading scales. The incidence of grade 3-5 toxicities will be reported. Patients will be assessed for toxicity as long as they are taking rucaparib, and patients will continue to be followed if rucaparib is discontinued for toxicity until the toxicities improve to grade 1 or resolve. Toxicities will be reported as a tabulated table by type and grade.

*PSA progression-free survival (PSA-PFS):*

A standard definition of PSA progression per PCWG3 will be used. PSA-PFS will be defined as an increase in 25% over a nadir value, confirmed by a follow-up PSA at least 4 weeks later. If patients are removed from study prior to PSA progression, then they will be censored at that time. We will use the Kaplan-Meier method to estimate the median PSA-PFS.

*Radiographic progression-free survival (PFS):*

Progression-free survival will be measured from the time of first dose to objective clinical or radiographic tumor progression as defined by PCWG3 for progressive disease

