### 2.2 Secondary Objectives

- Safety/Tolerability, defined as incidence of CTCAE v5.0 grade  $\geq 3$  toxicities experienced by patients on the trial.
- PSA progression-free survival, defined as a time from initiation on rucaparib therapy until PSA increase of 25%, confirmed with another measurement at least 4 weeks later (PCWG3).
- Progression-free survival: time to radiographic or clinical progression or death, whichever comes first. Based on RECIST version 1.1 and PCWG3 definitions including: 1. Progression of soft tissue lesions according to RECIST 1.1; 2. Progression of bony lesions detected by bone scan according to PCWG3 criteria; 2. Radiographically-confirmed spinal cord compression or pathological fracture due to malignant progression, or other clinical event deemed to be cancer-related.
- Objective response rate, defined as the proportion of patients with measurable disease at baseline, achieving a complete/partial response in target lesions (RECIST 1.1).

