#### 8.1.2 Secondary endpoints

8.1.2.1. *Safety:* this endpoint is defined as incidence of grade 3-5 toxicities based upon CTCAE v5.0 standard grading scales.

8.1.2.2. *PSA Progression-Free Survival (PFS):* PSA progression (PSA progression-free survival; PSA-PFS) will be defined per PCWG3 guidelines

For those subjects showing an initial decline in PSA from baseline, is defined as an increase in PSA that is ≥25% and ≥2 ng/mL above the nadir, and which is confirmed by a second value 3 or more weeks later (i.e., a confirmed rising trend).

For those subjects with no decline in PSA from baseline, is defined as an increase in PSA that is ≥25% and ≥2 ng/mL after 12 weeks.

8.1.2.3. *Radiographic Progression-free survival:* time to radiographic or clinical progression or death, whichever comes first. Based on RECIST version 1.1 and PCWG3 definitions including: Progression of soft tissue lesions according to RECIST 1.1; Progression of bone lesions detected with bone scan according to PCWG3 criteria; Radiologically-confirmed spinal cord compression or pathological fracture due to malignant progression, or other clinical event deemed to be cancer-related.

8.1.2.4 Objective response rate (metastatic disease only): defined as the proportion of patients achieving a complete/partial response in target lesions (RECIST

1.1)

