### **8.4.2 PSA**

Per the PCWG3, PSA progression is defined as the date that a 25% or greater increase and an absolute increase of 2 ng/mL or more from the nadir is documented and confirmed by a second value obtained 3 or more weeks later. Where no decline from baseline is documented, PSA progression is defined as a 25% increase from the baseline value along with an increase in absolute value of 2 ng/mL or more after 12 weeks of treatment.

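### PSA progression for the secondary PSA-PFS endpoint is defined in conflicting ways: the analysis section lacks the 2 ng/mL minimum and the 12-week rule that Section 8 sets out

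*Combined protocol and SAP*

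**What the plan says.** The event is described in six places, and each of them cites PCWG3.

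- **Section 10.1.2.2 (analysis).** It first says that the standard PCWG3 definition applies, then writes its own: "PSA PFS will be defined as an increase in 25% over a nadir value", confirmed by a further PSA at least 4 weeks apart. Men removed from study before PSA progression are censored at removal, and the median is estimated by Kaplan-Meier.
- **Synopsis, statistical method, secondary analysis.** The same rule: "PSA-PFS will be defined as an increase in 25% over a nadir value".
- **Synopsis, secondary endpoints, and Section 2.2.** Both run from the start of rucaparib "until PSA increase of 25%, confirmed with another measurement at least 4 weeks later". Neither says what the 25% is measured from.
- **Section 8.1.2.2 (definition of this endpoint).** After an initial decline, the rise must be at least 25% and at least 2 ng/mL above nadir, "which is confirmed by a second value 3 or more weeks later". A separate branch begins "For those subjects with no decline in PSA from baseline" and requires at least 25% and at least 2 ng/mL after 12 weeks.
- **Section 8.4.2 (progression criteria).** It requires "a 25% or greater increase and an absolute increase of 2 ng/mL or more from the nadir", confirmed at 3 or more weeks. With no decline it requires "a 25% increase from the baseline value along with an increase in absolute value of 2 ng/mL or more after 12 weeks of treatment".

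Only Section 8.4.2 names baseline as the reference for men without a decline. Neither Section 8 text states a confirmation step for those men.

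**The concern.** An analyst who programs the statistical section as written will use a different event from one who follows Section 8, and the plan does not say which section takes precedence. The trial has one arm, so there is no comparator in which a definitional shift would cancel out: the reported median means what the event rule makes it mean. If two rules remain, the choice can also be made after the data are seen.

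The population is exposed to the difference. Section 3.3 admits men with PSA as low as 2.0 ng/mL. A man who meets the primary endpoint has halved his PSA, so any responder with a baseline below 16 ng/mL has a nadir below 8, which is where the two rules part.

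**Working it through.** **1. The plan's own figures.** The plan states no assumed value for PSA-PFS. Its only design figures belong to the primary endpoint (Section 10: stop at 6 or fewer of 12; promising at 18 or more of 28; 50% against 75%). An exact binomial calculation gives early stopping 0.613 (stated 0.61), type I error 0.0815 (limit 0.1) and power 0.902 (stated 90%). They reproduce, and the PSA-PFS rule does not enter them.

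**2. The rules side by side.**

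| Element | 10.1.2.2 and synopsis analysis text | 2.2 and synopsis endpoint text | 8.1.2.2 and 8.4.2 |
|---|---|---|---|
| Relative rise | 25% over nadir | 25%, reference not named | at least 25% over nadir |
| Absolute rise | none | none | at least 2 ng/mL |
| Confirmation | 4 or more weeks, every man | 4 or more weeks, every man | 3 or more weeks after a decline; not stated without one |
| No decline | no rule | no rule | at least 25% and 2 ng/mL, after 12 weeks |

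**3. Trigger value.** For nadir N, Section 10.1.2.2 fires at 1.25N. Section 8 fires at the larger of 1.25N and N + 2. They agree when 0.25N is at least 2, that is, when N is 8 ng/mL or more.

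| Nadir (ng/mL) | 10.1.2.2 | Section 8 |
|---|---|---|
| 1 | 1.25 | 3.0 |
| 2 | 2.5 | 4.0 |
| 4 | 5.0 | 6.0 |
| 8 | 10.0 | 10.0 |

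**4. Time from nadir to trigger.** Time = doubling time × log2(trigger/N). The documents give no regrowth rate on treatment, so doubling times of 3, 6 and 9 months are assumed. A 25% rise takes 1.0, 1.9 and 2.9 months at any nadir. The Section 8 trigger takes:

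- nadir 1: 4.8, 9.5 and 14.3 months
- nadir 2: 3.0, 6.0 and 9.0 months
- nadir 4: 1.8, 3.5 and 5.3 months
- nadir 8 or more: the same as the 25% rule

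For one man the gap therefore runs from zero (nadir 8 or more) to 14.3 − 2.9 = 11.4 months (nadir 1, 9-month doubling).

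**5. Men without a decline.** Here baseline is assumed to serve as the nadir under Section 10.1.2.2. A 25% rise takes 4.2, 8.4 and 12.6 weeks at the same doubling times, so with PSA every 4 weeks it is first seen at weeks 8, 12 and 16.

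- Baseline 8 or more: Section 8 gives weeks 12, 12 and 16 if the week-12 draw counts as after 12 weeks, and otherwise week 16 in all three cases.
- Baseline 2: PSA must reach 4.0, one full doubling (13.04, 26.1 and 39.1 weeks), first seen at weeks 16, 28 and 40.

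**6. Confirmation, which can work the other way.** Visits are 28 days apart with ±3 days at each end (Section 5.2), so gaps run from 28 − 6 = 22 to 28 + 6 = 34 days. Of the 7 × 7 = 49 offset pairs, 21 give a gap under 28 days and none gives one under 21. A rise followed by a 22- to 27-day gap is confirmed under the 3-week rule but not under the 4-week rule; the man must wait for another PSA, or is censored if removed first. Separately, a man without a decline who has a single unconfirmed rise of at least 25% and 2 ng/mL after 12 weeks is an event under Section 8.4.2 as written, but not under Section 10.1.2.2.

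**The case against.** The best defence is that Section 10.1.2.2 opens by adopting the PCWG3 definition, that Section 8 writes that definition out twice with the same 25%, 2 ng/mL and 12-week elements, and that the other texts are shorthand for it. That is a fair account of what was probably intended, and it makes this a matter of harmonising text. It does not remove the conflict. The sentence after the PCWG3 reference sets out an explicit event with a different threshold and a different confirmation interval, and literally applied it counts a rise from 1.0 to 1.25 ng/mL as progression.

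It might also be said that removal from treatment would hide the gap. The PSA removal rule in Section 6.4 is a confirmed doubling from baseline. With baseline at least 2.0 and nadir no higher than baseline, neither N + 2 nor 1.25N exceeds twice baseline, so the Section 8 trigger is met no later than that doubling. This rule does not mask the difference.

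Other parts of the defence stand. The endpoint is secondary and descriptive, with no test or decision threshold. Any figure for the shift in the median would need a PSA distribution, nadir depth, regrowth rate and censoring pattern that the documents do not supply. Simply pasting in Section 8.4.2 would drop the confirmation that Section 10.1.2.2 now asks of men without a decline.

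**Conclusion.** The definitions conflict and should be reconciled before PSA-PFS is analysed. The threshold difference is plain arithmetic: the Section 10.1.2.2 trigger is lower whenever the nadir is below 8 ng/mL. The times in the working rest on assumed doubling times and illustrate single patients only.

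A reader might infer that following Section 10.1.2.2 always dates progression earlier. It usually does, but its universal 4-week confirmation can delay or censor some men whom Section 8.4.2 counts. A reader might also infer that the reported median must be badly understated. The documents do not support that: the size depends on entry PSA and nadirs, which they do not give, and may be near nil if most men enter with high PSA. Nor does the point reach the primary PSA50 endpoint, the two-stage rule or the sample size.

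**What to change.** Replace the PSA-PFS wording in Section 10.1.2.2, Section 2.2 and both synopsis texts with the Section 8.4.2 definition: a rise of 25% or more and 2 ng/mL or more over nadir, confirmed at 3 or more weeks; with no decline, 25% and 2 ng/mL over baseline after 12 weeks. Name baseline in Section 8.1.2.2 as well. Then state three things explicitly:

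1. Whether the rise in a man without a decline needs confirmation. Keeping the confirmation that Section 10.1.2.2 now requires of every man, at 3 or more weeks, is the natural choice.
2. Whether the week-12 draw counts as after 12 weeks.
3. Whether the end-of-treatment PSA (Section 5.5, 28 ± 3 days after the last dose, so 25 to 31 days) can confirm a rise before the man is censored at removal.

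The 3-week interval suits the schedule, because every permitted gap between 28-day visits is at least 22 days. The cost is wording only. The PSA values are already scheduled each cycle (optionally every 3 months after 12 months on treatment) and at the end-of-treatment visit.

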1.1 and PCWG3 definitions including: Progression of soft tissue lesions according to RECIST 1.1; Progression of bone lesions detected with bone scan according to PCWG3 criteria; Radiologically-confirmed spinal cord compression or pathological fracture due to malignant progression, or other clinical event deemed to be cancer-related

- Objective response rate, defined as the proportion of patients with measurable disease achieving a complete/partial response in target lesions (RECIST 1.1).

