or death, and summarized using a Kaplan-Meier curve. Progression will be assigned to the earliest observed time. Patients whose disease has not progressed at follow-up will be censored at the date when the last tumor assessment determined a lack of progression. We will use the Kaplan-Meier method to estimate the median PFS.

*Objective response rate:*

The objective response rate is defined as the percentage of patients with measurable disease at baseline who achieve an objective response by RECIST1.1 criteria (i.e. Complete response or Partial Response) to rucaparib. We will estimate the objective response rate, along with the exact 95% confidence interval, for the population of patients.

Sample size/Power calculation:

The sample size is calculated to detect an improved PSA50 response rate from 50% to 75%. An optimal Simon two stage design is planned. A total of 12 patients will be entered in the first stage and the data analyzed for futility 12 weeks after the last patient begins rucaparib treatment. If 6 or fewer subjects have a PSA response, the study will be terminated and we will conclude the regimen is ineffective. If  $\geq 7$  subjects respond, then an additional 16 patients will be studied, for a total of 28 patients. If a total of 17 or fewer subjects respond in stage one and two combined, we consider this regimen ineffective. If a total of 18 or more respond, we conclude the regimen is promising and warrants further study. The maximum sample size will be increased to 30 patients to account for possible dropouts. The total number of patients allowed with a non-*BRCA1* or -*BRCA2* mutations will be capped at 10. This will ensure that at least 20 men will be enrolled with *BRCA1/BRCA2* mutations.

This design provides 90% power to detect an absolute 25% increase in PSA response rate with a one-sided type I error of 0.1. The probability of early stopping is 0.61 under the null hypothesis that the PSA response rate is 50%.

---

Safety analysis	Standard safety summaries will be provided for treatment exposure, patient disposition, adverse events leading to discontinuation, serious adverse events, and all events resulting in death, including those up to 30 days after treatment discontinuation. The incidence of adverse events will be tabulated and reviewed for potential significance and clinical importance.
-----------------	---

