### 6.4 Removing Patients from the Protocol

In the absence of treatment delays because of adverse events, treatment will continue for until one of the following criteria applies:

- Patient decision. The patient is at any time free to discontinue treatment, without prejudice to further treatment
- Severe non-compliance with the study protocol
- Bone marrow findings consistent with myelodysplastic syndrome (MDS)/acute myeloid leukaemia (AML)
- Potential Hy's Law cases (AST or ALT  $\geq 3 \times$  ULN and TBL  $\geq 2 \times$  ULN with no other reason)
- PSA doubling from baseline value, confirmed by a second value at least 4 weeks apart, with a minimum time since initiation of therapy of 12 weeks.
- Disease progression by symptomatic or radiographic assessment. Patient requiring palliative radiation therapy will be considered to have disease progression and removed from the study.
- Intercurrent illness that prevents further administration of treatment
- Unacceptable adverse events that may or may not be directly related to treatment but that, in the judgment of the treating physician, makes it dangerous for the patient to be retreated.
- Adverse events requiring cessation of rucaparib, with inability to restart therapy within 14 days.
- General or specific changes in the patient's condition that render the patient unacceptable for further treatment, in the judgment of the investigator

Because an excessive rate of withdrawals can render the study uninterpretable, unnecessary withdrawal of patients should be avoided. When a patient discontinues treatment early, the investigator should make every effort to contact the patient and to perform a final evaluation. The reason(s) for withdrawal should be recorded.

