#### *10.1.2.3. Radiographic progression-free survival (rPFS)*

Progression-free survival will be measured from the time of first dose to objective tumor progression as defined by RECIST 1.1 for progressive disease or death and summarized using a Kaplan-Meier curve. Progression will be assigned to the earliest observed time. Patients whose disease has not progressed at follow-up will be censored at the date when the last tumor assessment determined a lack of progression.

We will use the Kaplan-Meier method to estimate the median PFS.

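### Section 10.1.2.3 gives rPFS a different event set from section 8.1.2.3, section 2.2 and the synopsis, and the endpoint called PSA progression-free survival is a time to PSA progression

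*Combined protocol and SAP*

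**What the plan says.** **rPFS.** Section 10.1.2.3 measures from first dose to "objective tumor progression as defined by RECIST 1.1 for progressive disease or death". The matching sentence in the synopsis (statistical methods) measures to "objective clinical or radiographic tumor progression as defined by PCWG3 for progressive disease" and continues "or death, and summarized using a Kaplan-Meier curve". The synopsis endpoint list, section 2.2 and section 8.1.2.3 agree with each other. They count RECIST 1.1 soft-tissue progression, bone progression (synopsis: "Progression of bone lesions detected with bone scan according to PCWG3 criteria"), cord compression, pathological fracture, other cancer-related clinical events, and death. Section 8.2 says that RECIST and PCWG3 are used in combination.

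**PSA-PFS.** The synopsis (endpoint list and methods) and sections 2.2, 8.1.2.2 and 10.1.2.2 all make a PSA rise the only event. None lists death or any other progression. Section 10.1.2.2 and the synopsis methods add the same rule: "If patients are removed from study prior to PSA progression, then they will be censored at that time". The median is estimated by Kaplan-Meier.

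**Removal.** The synopsis stops treatment at the first of PSA, clinical or radiographic progression. Section 6.4 lists "Disease progression by symptomatic or radiographic assessment" as a reason for removal and adds: "Patient requiring palliative radiation therapy will be considered to have disease progression and removed from the study".

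**The concern.** For rPFS, the analysis section and the endpoint definition name different events, and an analyst will program from the analysis section. The man who needs palliative radiation shows the gap. Under 8.1.2.3 he has clinical progression and is an event. Under 10.1.2.3 he has no RECIST progression, and the censoring sentence there covers only men whose disease has not progressed, whereas section 6.4 says that his has. His status is undefined.

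For PSA-PFS, the same man is censored in a curve whose name says progression-free survival. The reported median could be read as time alive without progression, in a trial for men who are ineligible for ADT or have declined it. It is instead the time to one kind of progression, with the others treated as censoring.

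**Working it through.** The documents give no median, event count or rate for either endpoint, so there is no stated figure to reproduce. The only stated operating characteristics belong to PSA50, and they hold: with 6 or fewer of 12 as the stopping rule and 18 or more of 28 as success, exact binomial sums give early stopping 0.613 at a 50% response rate (stated 0.61), power 0.902 at 75% (stated 90%) and type I error 0.081 (limit 0.1). Nothing below alters them.

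**1. rPFS event sets side by side**

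| Event | 8.1.2.3, 2.2, synopsis | 10.1.2.3 |
|---|---|---|
| RECIST 1.1 soft-tissue progression | event | event |
| Death | event | event |
| Clinical progression alone | event | not an event; censoring not stated |
| Bone progression | PCWG3 bone-scan rule | only through RECIST new-lesion and nontarget rules |

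Neither set contains the other. Bone lesions are nonmeasurable (8.2.3) and hence nontarget (8.2.6). Tables 5 and 6 make one new lesion progression, and 8.2.7, which requires the finding to be unequivocal, discusses bone lesions under that rule. PCWG3 as written in 8.4.3 needs at least 2 new lesions, then at least 2 more on a later scan. A single unequivocal new bone lesion is thus an event under 10.1.2.3 but not under 8.1.2.3 read with 8.4.3.

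Let L be the total hazard of 8.1.2.3 events, c the share of it lost under 10.1.2.3 (those men being censored), and e the extra RECIST-only hazard as a share of L. With independent constant hazards the medians are ln2/L under 8.1.2.3 and ln2/[L(1 - c + e)] under 10.1.2.3. The ratio, 10.1.2.3 over 8.1.2.3, is 1/(1 - c + e). Both shares are assumptions:

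- c = 10%, e = 0: 1/0.90 = 1.11
- c = 25%, e = 0: 1/0.75 = 1.33
- c = e: 1.00
- c = 10%, e = 25%: 1/1.15 = 0.87

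If the analyst counts clinical-only events anyway, their contribution to c is zero.

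**2. The bone-scan wording that the 8.1.2.3 event set relies on**

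- 8.2.5: 2 or more new lesions; check with another imaging modality if flare or trauma is suspected; confirmation generally not needed when many new areas appear.
- 8.3.3: confirm progression seen at the first scheduled assessment with a second scan at least 6 weeks later, unless soft-tissue disease or symptoms are clearly worsening.
- 8.4.3: a confirmatory scan at least 6 weeks later is required, with at least 2 additional new lesions.

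Sections 8.2.5 and 8.4.3 conflict for the man with many new areas of uptake.

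**3. PSA-PFS**

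Let q be the share of first events that are not PSA progression, assumed to be 10% to 25%. PSA is measured monthly and scans are every 3 or 6 months, so PSA will often come first. With independent constant hazards, total rate L and PSA rate (1 - q)L:

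- PSA-PFS median: ln2/[(1 - q)L]. Median to any progression or death: ln2/L. Ratio 1/(1 - q) = 1/0.90 = 1.11, or 1/0.75 = 1.33.
- Alive and free of any progression when the PSA-PFS curve reads 50%: 0.5^(1/(1 - q)) = 0.463 or 0.397.
- Cumulative incidence of PSA progression as first event at that time: (1 - q)(1 - 0.463) = 0.483 at q = 10%; (1 - q)(1 - 0.397) = 0.452 at q = 25%.
- Men with a non-PSA first event, if all 28 have one: 28 × 0.10 = 2.8; 28 × 0.25 = 7.

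For scale, the sampling SD of a Kaplan-Meier median with 28 men, exponential times and no censoring is 1/(ln2 × √28) = 0.273 of the median.

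**The case against.** On PSA-PFS, every definition counts only a PSA rise, and the censoring rule is identical in both places where it appears. The analyst has one reading. A single-cause median that exceeds an any-event median is arithmetic, and progression and death are reported separately as rPFS. The shares q, c and e have no source. Eligibility points to few early deaths or clinical-only events: life expectancy of at least 12 months, no visceral metastases over 3 cm, no bone pain needing narcotics, and biochemically recurrent men included. An 11% shift is less than half of the 27% sampling SD. On rPFS, section 8.2 could be taken to mean that 10.1.2.3 is shorthand for the combined criteria.

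Most of this stands and limits the weight of the point. It does not make the PSA-PFS label correct or say how death is handled. Nor does it settle rPFS: the synopsis and 10.1.2.3 carry nearly the same sentence and differ in the event definition itself, so the analyst cannot tell which governs.

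A reader might infer more in four places, without support:

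- That 10.1.2.3 can only lengthen the rPFS median. The single-new-lesion rule can shorten it.
- That 10.1.2.3 discards all bone progression. The new-lesion and nontarget rules keep some of it.
- That 10.1.2.3 censors men with clinical-only progression. It is silent.
- That the PSA-PFS median is biased upwards by informative censoring. As a time to PSA progression it is unbiased if the causes are independent, and too long only if they are positively correlated. The documents show neither.

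**Conclusion.** Both points hold on the text. Section 10.1.2.3 contradicts section 8.1.2.3, section 2.2 and the synopsis on what counts as an rPFS event, and it leaves clinical-only progression undefined. The direction and size of the effect on the median are unknown; the illustrative ratios run from 0.87 to 1.33 on assumed shares. PSA-PFS is a cause-specific time to PSA progression. Its median exceeds the median to any progression or death by a factor of 1.11 to 1.33 if q is 10% to 25% and hazards are constant and independent. That is a difference in the quantity reported, of the order of sampling error at this sample size, and not a demonstrated bias. Confidence is high in the textual findings; the sizes are illustrations only. Both endpoints are descriptive and secondary, so this should be corrected before analysis but does not threaten the primary conclusion.

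**What to change.** - **Section 10.1.2.3:** use the 8.1.2.3 event set, as the synopsis does, so that clinical progression alone has a defined status.
- **Sections 8.2.5, 8.3.3 and 8.4.3:** reconcile when bone-scan progression needs confirmation, by what means, and whether additional lesions are required. State how bone progression still unconfirmed at removal is analysed.
- **Section 10.1.2.2 and synopsis:** either rename the endpoint time to PSA progression and state how death and other progression are handled (a cumulative incidence with both as competing events would do), or keep the name and count both as events.

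The cost is wording and at most one additional table, from data already collected, with no change to sample size or visits. Keeping the name and counting the other events gives a shorter median: multiplied by 1 - q, so a 12-month median would become 12 × 0.90 = 10.8 months at q = 10% or 12 × 0.75 = 9.0 months at q = 25% (the 12 months is illustrative).

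The different windows for the off-treatment scan (prior month in Table 1 footnote b, prior 3 months in sections 5.5 and 5.6) are a separate point to reconcile.
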